2.2.3 Additional Data of Interest

Additional information is collected to characterize the study population, implanted system, and progress of the clinical investigation. These include demographics, medical history, cardiovascular medications, ECG characteristics, implanted device information, device programming, Home Monitoring transmission success, non-Solia S LBB area related adverse events, reasons for inability to place or achieve capture with Solia S in LBB area, revisions to implanted systems, results for returned product analysis, compliance to protocol, and change in QOL scales.

2.2.4 Other Planned Analyses

Other planned analyses include subgroup analysis (age ≥ 65 years), poolability analysis to assess the primary outcomes across sites and regions (U.S. and outside of U.S.), and analyses to determine differences in outcomes based on sex and race.

3 General Analysis Considerations

The planned analyses described here will be performed when the data required to complete the analysis is available. A pivotal analysis and interim report of primary endpoint 1 and primary endpoint 2 is planned and will support other analysis required for a PMA submission. Analysis of secondary endpoint 1 and subgroup analysis will be performed after all patients have completed the 12-month study visit or exited the study.

For annual progress reports, the results of completed analyses will be provided when available. If the planned analysis time point has not yet been met, progress toward the analysis and current available data will be presented using descriptive statistics within the annual progress report.

3.1 Statistical Methods

Descriptive statistics will be used to present and summarize the data collected in the clinical study. Frequency distributions (counts and percentages) and cross tabulations will be

presented for discrete variables. Means, standard errors, and ranges will be presented for continuous variables. Proportions will be calculated using known non-missing values. All statistical tests and/or confidence intervals will be performed at $\alpha = 0.05$ (2-sided).

For reporting of adverse events, descriptive statistics that describe the percentage of subjects experiencing an adverse event and rate of adverse event as events per subject-year will be provided. The total number of ITT subjects and cumulative duration of follow-up completed for the subjects as of the date of the report will be utilized to calculate the descriptive statistics.

Analysis of SADE-free rates for Solia S and procedure related events will be based on Clinical Events Committee (CEC) adjudicated event data. Analysis of the rest of the endpoints will be based on site-reported data.

3.2 Analysis Populations

All clinical data will be analyzed based upon the pre-defined analysis populations as outlined in Table 1. Additional analysis population considerations for specific analysis are included within the analysis method details (Section 4).

Table 1: Study Analysis Populations

Analysis Population	Definition
Intent-to-Treat (ITT) – Primary Endpoint 1 (Safety), Secondary Endpoint 2	This ITT population is defined as 
 • all enrolled subjects (subjects with successfully implanted Solia S in the LBB area) and • subjects with an unsuccessful implant attempt of the Solia S in the LBB area who had a qualifying primary safety endpoint event prior to their exit from the study.
Intent-to-Treat (ITT) – Primary Endpoint 2 (Efficacy)	This ITT population is defined as 
 • all enrolled subjects (subjects with successfully implanted Solia S in the LBB area) and • subjects with an unsuccessful implant attempt of the Solia S in the LBB area.
Intent-to-Treat (ITT) – Secondary Endpoint 1 (QOL), Secondary Endpoints 3-5	This ITT population is defined as 
 • all enrolled subjects (subjects with successfully implanted Solia S in the LBB area)

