2.2.1 Primary Endpoints

Primary Endpoint 1: Serious adverse device effect (SADE)-free rate through 3 months post-implant

The purpose of primary endpoint 1 is to evaluate the overall incidence of serious Solia S LBB lead related adverse device effects and serious implant procedure events related to the Solia S LBB lead that occur through 3 months post-implant. The parameter of interest is the Solia S LBB lead complication-free rate, which will be calculated as the number of subjects without one or more complications divided by the total number of study subjects successfully enrolled and subjects undergoing an unsuccessful implant attempt who have a qualifying primary safety endpoint event in percent.

Primary Endpoint 2: Implant success

The purpose of primary endpoint 2 is to evaluate the implant success rate of the Solia S lead in the LBB area. The parameter of interest is the percentage of subjects with Solia S placed successfully in the LBB area divided by the total number of consented study subjects in whom an implant of Solia S in the LBB area was attempted. The definition of implant success is provided in Section 4.1.2.

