4.1 Endpoint Analyses

4.1.1 Primary Endpoint 1 - Serious Adverse Device Effect (SADE)-Free Rate Through 3 Months Post-Implant

The purpose of primary endpoint 1 is to evaluate the serious lead related adverse device effects related to Solia S lead utilized or attempted to be implanted in the LBB area and

serious implant procedure events related to the Solia S LBB lead that occur through 3 months post-implant.

The following hypotheses have been defined to evaluate the primary endpoint "Serious adverse device effect (SADE)-free rate through 3 months post-implant":

H_0 : The serious adverse device effect (SADE)-free rate through 3 months post-implant is less than or equal to 87.5%

$$\text{SADE-free rate} \leq 87.5\%$$

H_a : The serious adverse device effect (SADE)-free rate through 3 months post-implant is greater than 87.5%

$$\text{SADE-free rate} > 87.5\%$$

Primary endpoint 1 will be evaluated by performing an exact, one-sided binomial proportion test comparing the observed proportion (overall SADE-free rate through 3 months) to the performance goal of 87.5%. The lower, two-sided 95% confidence bound for the overall SADE-free rate must be greater than 87.5% to reject the null hypothesis (H_0), which would demonstrate evidence that the SADE-free rate is significantly higher than 87.5%.

For the primary endpoint 1 analysis, ITT population subjects who have at least 76 days of follow-up (corresponding to the earliest potential in-window 3-month visit) or experienced the primary safety endpoint will be included. A Kaplan-Meier survival analysis (time-to-event) for the primary endpoint outcome will also be performed.

Subjects without a primary safety endpoint event with less than 76 days of follow-up will be excluded from the Kaplan-Meier survival analysis and the binomial proportion test to avoid overestimation of the SADE-free rate.

Sample Size Determination for Primary Endpoint 1

Prior studies evaluating the safety of Solia S when implanted in the right ventricle has demonstrated a high SADE-free rate, between 94.3% and 98.5% (Master Study of the Siello Pacemaker Lead and Siello IDE Clinical Study, data on file). When implanting in the LBB area, the expected safety needs to consider the change in implant location. A summary of published data that includes safety information for leads implanted in the LBB area is presented in Table 2.

Table 2: LBB Area Pacing—Published Safety Results

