Study	Mean Follow-up Duration (months)	Total Implanted Subjects (n)	Subjects without SADE (n)	SADE-Free Rate	95% CI – Lower Bound
Su L et al. 2021	18.6	618	600	97.1%	95.4%
Vijayaraman P et al. 2019	5.2	93	87	93.6%	86.4%
De Pooter J et al. 2021	3.0	44	39	88.6%	75.6%
Li X et al. 2019	3.0	30	29	96.6%	81.9%

Based on this information, it is anticipated the Solia S lead will have a safety profile similar to published literature for leads implanted in the LBB area with an expected SADE-free rate of at least 93.0%. The assumed performance (93%) and performance goal of 87.5% are compared to the published safety results in Figure 1.

[figure not shown]

Figure 1: Assumed Safety Performance Compared to Published Results

The estimated sample size required to evaluate primary endpoint 1 is based on a superiority comparison of overall Solia S lead serious adverse device effect free-rate to 87.5% through 3 months post-implant. The sample size for primary endpoint 1 was calculated based on the following assumptions.

- Study Design: Non-randomized
- Type I error (alpha): 0.025 (one-sided for superiority)
- Statistical power: 80%
- Performance Goal for SADE-Free Rate through 3 months post-implant: 87.5%
- Expected SADE-Free Rate through 3 months post-implant: 93% (Based on Literature Review/Master Study)
- Test basis: Exact binomial test
- Attrition Rate: 5%

For primary safety endpoint 1, a total of 247 evaluable Solia S leads would be required to demonstrate superiority to a SADE-free rate of 87.5%. Assuming a 5% attrition rate, a total of 260 (= 247 / 0.95) patients with a Solia S lead would be required to be enrolled to evaluate Primary Safety Endpoint 1.

Justification of Pooling for Primary Endpoint 1

Justification of pooling data from other prospectively collected data sources will include the following considerations:

- Design of study including but not limited to inclusion/exclusion criteria, follow-up visit schedule, and required procedures/data collection
- Implanted devices included in the study
- Criteria for success of Solia S LBB area implants
- Study organization and level of monitoring
- Availability of subject level data and, when required, documentation supporting reported adverse events

Data from studies that are determined to be similar to BIO-CONDUCT with regards to the considerations above may be pooled for analysis of primary endpoint 1. A poolability analysis will be conducted to examine heterogeneity (Section 4.4).

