Specifically, it is planned that for evaluation of primary safety endpoint 1, data from subjects in the BIO|MASTER.Selectra 3D study (NCT04323670) with a successful Solia S lead LBB area implant will be pooled with data from the BIO-CONDUCT study. The BIO|MASTER.Selectra 3D study was a multi-center, prospective, non-randomized post-market study designed to evaluate the clinical safety, performance, and handling of the Selectra 3D catheter when used for conduction system pacing implants (His bundle or LBB area) of the Solia S lead. Additionally, performance and safety of the Solia S lead was collected. A total of 157 subjects were enrolled into the BIO|MASTER.Selectra 3D study from October 8, 2020 to November 18, 2021 across 10 study sites in Europe, Asia, and Australia.

Only subjects enrolled into the BIO|MASTER.Selectra 3D study with a successful Solia S lead LBB area implant and at least 76 days of follow-up or with a Solia S lead LBB area implant attempt and qualifying primary safety endpoint event will be included in pooled analysis with the BIO-CONDUCT ITT population. All potential endpoint events occurring in the BIO|MASTER.Selectra 3D study (i.e., serious Solia S LBB lead events and serious procedure related events) will be adjudicated by the BIO-CONDUCT CEC and adjudication outcomes will be utilized for the analysis of primary endpoint 1.

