4.2 Analysis of Additional Data of Interest

Additional data of interest will be reported for the relevant ITT analysis population (i.e., safety additional data of interest will utilize the same ITT population as primary endpoint 1; lead implant information will utilize the same ITT population as primary endpoint 2; remaining additional data of interest will utilize same ITT population as secondary endpoints

1 and 3 -5). For each analysis, only subjects with the data of interest available at implant or visit will be included. Subjects for which data is not available will be excluded from the analysis.

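### Primary endpoint 1 counts failed-attempt subjects only if they had an event, so its rate is slightly conservative and the plan gives no per-attempt safety estimate

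*SAP*

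**What the plan says.** SAP 3.2, Table 1, defines the set for primary endpoint 1 as "all enrolled subjects (subjects with successfully implanted Solia S in the LBB area") together with "subjects with an unsuccessful implant attempt of the Solia S in the LBB area who had a qualifying primary safety endpoint event". SAP 2.2.1 builds the same rule into the rate, whose denominator is the "total number of study subjects successfully enrolled and subjects undergoing an unsuccessful implant attempt who have a qualifying primary safety endpoint event". The pooling text in SAP 4.1.1 applies it to the BIO|MASTER.Selectra 3D study: besides successful implants with at least 76 days of follow-up, only subjects "with a Solia S lead LBB area implant attempt and qualifying primary safety endpoint event will be included in pooled analysis". SAP 4.1.4 carries the rule to secondary endpoint 2, and SAP 4.2 says that "safety additional data of interest will utilize the same ITT population as primary endpoint 1". Only the primary endpoint 2 set in Table 1 contains every subject with an attempt.

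The protocol's definition of primary endpoint 1 starts observation at the first attempt to place the lead in the LBB area. SAP 4.1.1 adds a follow-up rule: "Subjects without a primary safety endpoint event with less than 76 days of follow-up will be excluded from the Kaplan-Meier survival analysis", and also from the binomial test.

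For sample size, SAP 4.1.1 gives "Expected SADE-Free Rate through 3 months post-implant: 93% (Based on Literature Review/Master Study"), a performance goal of 87.5%, one-sided alpha 0.025, 80% power and an exact binomial test. It concludes that "a total of 247 evaluable Solia S leads would be required to demonstrate superiority to a SADE-free rate of 87.5"%, raised to 260 for 5% attrition.

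**The concern.** A subject with a failed attempt is at risk from the first contact of the lead with the septum. If an event follows, the subject adds one to the denominator and nothing to the event-free count. If no event follows, the subject appears in neither. The resulting quantity is neither a rate per implanted subject nor a rate per attempted subject.

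Two things are at stake. First, someone asking how safe it is to try this lead in the LBB area gets no pre-specified answer, because the other safety summaries use the same set. A crude BIO-CONDUCT figure could be pieced together from planned outputs, but it is not planned, and the pooled study's event-free failed attempts are outside the analysed set. Second, the sample-size text does not say whether the 93% already allows for subjects who enter only because they had an event.

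**Working it through.** **Inputs.** Goal 87.5%, expected rate 93%, one-sided alpha 0.025, exact binomial test, 247 evaluable and 260 enrolled (SAP 4.1.1). Failed attempts: 3% to 12% (protocol 8.2.1); 12% also follows from the 88% success assumed in SAP 4.1.2; Table 3 pools to 88 of 1564 = 5.6%. The documents give no event rate for failed attempts, so 1% to 10% is an assumption.

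**Reproducing 247 and 260.** The normal approximation n = (1.96·√(0.875·0.125) + 0.8416·√(0.93·0.07))² / 0.055² gives 246.2, rounded up to 247. Then 247/0.95 = 260. Both match.

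**Power under the stated exact test.** At n = 247 the smallest passing count is 227 event-free, so 20 SADEs are allowed and the actual alpha is 0.0186. Power is P(Bin(247, 0.93) ≥ 227) = 79.2%.

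**Direction of the bias.** Let N be all attempts, I₀ the event-free implanted subjects and F₀ the event-free failed attempts. The per-attempt rate is (I₀ + F₀)/N and the planned rate is I₀/(N − F₀). Taking F₀ event-free subjects out of both numerator and denominator can only lower a proportion. The planned rate is also never above the implanted-only rate, since it adds only events to that rate's denominator.

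**Size of the bias.** With f the share of failed attempts, q their event rate and 93% event-free among implanted:

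- per-attempt rate A = (1 − f)·0.93 + f·(1 − q)
- planned rate B = (1 − f)·0.93 / [(1 − f) + f·q]

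For f = 12% and q = 7%: A = 93.0%, B = 0.8184/0.8884 = 92.1%, a gap of 0.88 points. For f = 3% and q = 7%: A = 93.0%, B = 0.9021/0.9721 = 92.8%, a gap of 0.20 points. Across q = 1% to 10% the gap is 0.20–0.21 points at f = 3%, 0.38–0.39 at 5.6% and 0.85–0.89 at 12%. It hardly depends on q.

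**Type I error.** If every attempt has a true rate of 87.5%, the planned analysis with 247 implanted passes with probability 1.2% at 3% failed and 0.3% at 12% failed, both below 2.5%.

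**Power if 93% describes implanted subjects only.** With k failed-attempt events added to 247 implanted, the test is run at n = 247 + k. The total number of SADEs allowed stays at 20 for n = 247 to 251, is 21 for n = 252 to 260, and is 22 at 261. Power at 93%:

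| Failed-attempt events | 247 implanted | 260 implanted |
|---|---|---|
| 0 | 79.2% | 79.3% |
| 1 | 71.8% | 79.3% |
| 2 | 63.1% | 72.0% |

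With 260 implanted, the first such event moves n to 261, where one more SADE is allowed, so it costs nothing. At a true 95% and 247 implanted, power is P(Bin(247, 0.95) ≥ 228) = 97.6% with one event and P(Bin(247, 0.95) ≥ 229) = 95.7% with two.

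**Which population does 93% describe?** Table 2 is headed by implanted subjects. Its denominators 618, 93, 44 and 30 equal the successful-implant counts of the corresponding studies in Table 3. That points to implanted subjects, but it does not show whether the published event counts include failed attempts.

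**The case against.** The rule is explicit, applied consistently and conservative, and it fits the SAP's stated wish not to overestimate the SADE-free rate. That stands, and it is why the primary set should remain.

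A reader might infer that the study is underpowered because 93% excludes failed-attempt events. The documents do not support that. On its face, 93% is the expected value of the endpoint as defined, and that definition includes failed-attempt events. The cited studies' handling of failed attempts cannot be seen. The SAP words 93% as a minimum, while Table 2 pools to 755/785 = 96.2%. Any power averaged over failed attempts needs an event rate that the documents do not give. The loss also depends on where n falls on the critical-value steps, as the 260 column shows.

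A reader might equally infer that all attempts should be the primary set. That would be worse if failed attempts leave early without events. If implanted leads were truly 87.5% SADE-free and failed attempts showed 0–3% SADEs, a crude all-attempts proportion would pass about 3%, 4% or 7–10% of the time at 3%, 5.6% or 12% failed. The planned set would pass 1.2–1.9% of the time.

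Finally, a subject without an LBB-area lead cannot later have that lead dislodge, so a censored Kaplan-Meier estimate is not a pure per-attempt risk. This limits the supportive analysis but does not remove its use. The protocol text available for this review begins partway through the endpoint definition, so the absence of a rationale or allowance is claimed for the SAP only.

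**Conclusion.** The point holds as a minor one. The denominator of primary endpoint 1 depends on the outcome, and the planned rate and curve lie below the per-attempt rate by about 0.2 to 0.9 percentage points at 3% to 12% failed attempts. This assumes 93% among implanted subjects and changes little for failed-attempt event rates of 1% to 10%. The direction is conservative and type I error is not inflated. What is missing is a planned estimate of safety per attempt.

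On power, the firm statement is that the exact test with 247 evaluable subjects gives 79.2% at 93%, slightly below the stated 80%. The further loss from failed-attempt events is conditional on 93% being an implanted-only figure, and it is small if the true rate is 95% or more.

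**What to change.** Keep the primary set and the success rule.

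1. In SAP 4.1.1, pre-specify one supportive Kaplan-Meier estimate of primary endpoint 1 in all BIO-CONDUCT subjects with an implant attempt (the primary endpoint 2 set). Time starts at the first attempt, and event-free failed attempts are censored at exit instead of excluded. Do the same for the pooled study where attempt-level data exist.
2. Attach no success rule. State two limits beside it: censoring applies implanted subjects' later lead risk to subjects who have no LBB-area lead, and a crude all-attempts proportion can overstate safety if failed attempts exit early.
3. Restate power at 247 as 79.2% under the exact test, and say which population the 93% describes. If it is implanted subjects only, add the power with one and two failed-attempt events: 71.8% and 63.1% at 247 implanted, 79.3% and 72.0% at 260. Label any averaged figure as resting on an assumed event rate.

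The cost is a few sentences in the SAP and one supportive curve. The BIO-CONDUCT subjects are already counted for primary endpoint 2. The downside is a slightly less favourable stated power.

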3.3 Handling of Missing Data

All reasonable methods will be taken to ensure a minimum of missing data, including site monitoring, training, and corrective actions, if required, ongoing review of collected data for accuracy and completeness, and repeated, documented attempts to contact subjects with missing study visits. Any reasons for missing data or withdrawal from the study will be documented when possible.

If warranted, the impact of missing data on conclusions about the primary study endpoints will be examined in sensitivity analyses, which may include multiple imputation methods.

For secondary endpoint 1, missing QOL data at either the baseline or 12-month follow-up visit affects the number of subjects that can be included in the analysis. It is anticipated that subjects may either forget or choose not to answer one or more of the questions in the QOL. In some cases, subjects may also provide two answers for one or more of the questions. There is no appropriate method to correct these QOL questionnaires after the subject completes the visit.

If needed to ensure sufficient subjects to analyze secondary endpoint 1, an analysis using the last observation carried forward principle and/or average replacement for missing QOL answers or QOL questions with multiple answers may be performed. Additionally, last observation carried forward may be used in cases for which the QOL questionnaire is not completed at the 12-month visit. If there are more than 10% of subjects with missing answers, an assessment of the cause for the missing answers will be performed. If the assessment is such that a random cause can be assumed, then a multiple imputation technique that accounts for variability in imputation will be utilized. Additionally, where missing data are imputed, sensitivity analyses will be completed.

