# 18 Appendix A: Modifications to the Protocol

### **Protocol Version History**

Protocol Version	Summary of Changes since Previous Version
23-Feb-2022	Initial version submitted to sites
10-Aug-2022	
 
Protocol revisions include:
 
Addition of 12-month Follow-Up Visit
 
Addition of secondary endpoint 1: Quality of Life (QOL), associated statistical and sample size analyses, QOL data collection at the Enrollment Visit and 3-,6-, and 12-Month Follow-up Visits, and QOL administration details, and additional data of interest for change in QOL scales from pre-implant baseline to the 3-, 6-, and 12-month follow-up for scale changes not evaluated in secondary endpoint 1
 

, * 1	
 
Addition of collection of implanted system information and implant information, if applicable, at unsuccessful implants
 
Addition of collection of one 12-lead paced ECG from the time of the 3 or 6-month follow-up visits. Previously, an ECG was optional at follow-ups and collected only 'if available per standard of care'.
 

8	
 
The follow-up visit adverse event interview was clarified to allow for either an in-office or phone call interview with subjects. To allow for different visit scenarios, the specific definition of a remote follow-up was removed and device documentation requirements for in-office vs. remote follow-ups were made more general.
 

	
 
Addition of a Sub-group Analysis of the primary and secondary endpoints evaluating subjects ≥65 years of age
 
Exclusion Criteria "Patient is expected to receive a heart transplant within X months" and "Patient life expectancy is less than X months" were updated from 6 to 12 months
 

	Other minor revisions to improve clarity / streamline protocol

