4.1.3 Secondary Endpoint 1: Quality of Life (QOL) Through 12 Months Post-Implant

The purpose of secondary endpoint 1 is to evaluate the improvement in QOL for patients with successful Solia S lead implantation in the LBB area. Specifically, the physical function scale of the SF-36 will be used as it has been shown to be the best all-around measure of physical health (Ware JE Jr. et al. 2000). The QOL scale is standardized such that a higher score indicates better physical health.

The following hypotheses have been defined to evaluate the improvement in quality of life:

H_0 : The improvement in quality of life through 12 months post-implant for subjects with successful Solia S lead implanted in the LBB area is less than or equal to 2.8

$$\text{Improvement in QOL}_{\text{Physical Function Scale}} \leq 2.8$$

H_a : The improvement in quality of life through 12 months post-implant for subjects with successful Solia S lead implanted in the LBB area is greater than 2.8

$$\text{Improvement in QOL}_{\text{Physical Function Scale}} > 2.8$$

Secondary endpoint 1 will be evaluated by performing an exact one-sample t-test comparing the mean improvement in QOL from baseline to 12 months post-implant to the performance goal of 2.8. The lower, two-sided 95% confidence bound for the improvement in QOL must be greater than 2.8 to reject the null hypothesis (H_0), which would demonstrate evidence that the improvement in QOL is significantly higher than 2.8.

For the secondary endpoint 1 analysis, ITT population subjects with evaluable QOL paired baseline and 12-month measurements will be included. Subjects for which a baseline or 12-month physical function QOL score cannot be calculated, either due to missing or incomplete QOL data, will be excluded from the analysis.

Sample Size Determination for Secondary Endpoint 1

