Prior studies evaluating the quality of life in elderly patients receiving dual-chamber pacemakers with standard RV pacing have demonstrated modest improvement (ranging from 2.7 to 4; weighted mean of 2.8) in QOL as assessed by the SF-36 physical function scale from baseline (pre-implant) to 12 months post-implant (Fleischmann KE et al. 2006, Yu CM et al. 2014). More recently, Li H et al. (2021), found patients experiencing pacemaker-induced cardiomyopathy that were upgraded from RV pacing to LBB area pacing had a higher score in the physical function scale by 18.2 points at 12 months post-upgrade. At 24 months post-implant, in a crossover study, Kronborg MB et al. 2014 showed a 5-point improvement as measured by the physical function scale comparing His or para-His pacing to RV pacing. However, this improvement was not shown to be statistically significant. Other studies on conduction system pacing have noted improved QOL in patients receiving this therapy (Lustgarten DL et al. 2015, Occhetta E et al. 2006).

Based on this information, it is anticipated that patients with successful LBB area pacing with the Solia S lead will have an improvement in QOL, as measured by the SF-36 Physical Function score, of at least 10 from pre-implant baseline to 12 months post implant. This improvement in the Physical Function Score with LBB area pacing using a Solia S lead is the expected improvement due to receiving a pacemaker system (pre-implant baseline to RV pacing, average improvement in QOL score = 2.8) plus the additional expected benefit due to utilizing LBB area pacing as compared to RV pacing (expected improvement in QOL score = 7.8; combining LBB vs RVp from Li H et al. and Kronborg MB et al, weighted mean = 7.8). For the sample size calculation, an expected improvement in the Physical function Score was rounded to 10.

The estimated sample size required to evaluate secondary endpoint 1 is based on a superiority comparison of the improvement in QOL (physical function scale) to the expected improvement with RV pacing of 2.8 points. The sample size for secondary endpoint 1 was calculated based on the following assumptions.

Assumptions:

- Study Design: Non-randomized
- Type I error (alpha): 0.025 (one-sided for superiority)
- Statistical power: 80%
- Standard deviation: 30
- Performance Goal for QOL_{Physical Function Scale} Improvement: 2.8
- Expected QOL_{Physical Function Scale} Improvement: 10
- Test basis: Exact one-sample t-test

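### For the QOL endpoint, SAP 3.3 commits to multiple imputation only when missingness looks random and names no analysis when it does not, so completers can decide the test with no sensitivity analysis required

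*SAP*

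**What the plan says.** Secondary endpoint 1 is the one powered secondary endpoint (SAP 2.2.2) and is tested only if both primary endpoints succeed (SAP 3.5). Its population in SAP Table 1 is every subject with a successful implant in the LBB area. SAP 4.1.3 compares the "mean improvement in QOL from baseline to 12 months post-implant to the performance goal of 2.8", and the lower two-sided 95% bound must exceed that goal.

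Missing scores are covered in two places:

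- **SAP 4.1.3:** "Subjects for which a baseline or 12-month physical function QOL score cannot be calculated, either due to missing or incomplete QOL data, will be excluded". No exception is made.
- **SAP 3.3:** LOCF or average replacement may be used. If more than 10% of subjects have missing answers, the cause is assessed, and if "a random cause can be assumed, then a multiple imputation technique that accounts for variability in imputation will be utilized". The section does not define a random cause and says nothing about the opposite finding.

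On sensitivity analyses, SAP 3.3 has two sentences. One covers the primary endpoints, if warranted. The other says that "where missing data are imputed, sensitivity analyses will be completed".

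The protocol's version history (Appendix A) records "QOL data collection at the Enrollment Visit and 3-,6-, and 12-Month Follow-up Visits", so interim scores are available. SAP 3.3 does not name them as predictors for imputation.

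**The concern.** The plan orders an assessment and provides for only one of its two outcomes. If missingness is judged unrelated to health, multiple imputation follows. If it is judged related to health (subjects too ill to attend, or withdrawn), the commitment lapses and 4.1.3 governs, which means completers.

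A completer mean represents all implanted subjects only if missingness is unrelated to the change in score. Imputation from baseline and interim scores also copes with missingness that those scores explain. The non-random case is therefore the one in which the completer mean is least dependable, and it is the case left without a named method. If subjects are excluded and nothing is imputed, the second sensitivity sentence is not triggered and the first does not cover this endpoint.

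At stake is a formally tested claim. If subjects who do worse drop out, a test meant to run at 2.5% one-sided runs at a higher rate.

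**Working it through.** **Inputs from SAP 4.1.3:** "Type I error (alpha): 0.025 (one-sided for superiority"); "Statistical power: 80"%; "Standard deviation: 30"; goal 2.8; expected improvement 10; one-sample t-test; 139 pairs.

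**Reproducing the plan's figure.** The difference is 10 − 2.8 = 7.2. Under the noncentral t distribution with SD 30 and one-sided 0.025, power is 79.9% at n = 138 and 80.2% at n = 139. The planned 139 reproduces.

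**Assumptions, not in the documents:** share missing m = 10% (the SAP's own trigger) or 20%, and a gap D by which the missing subjects' mean change lies below the completers'. I use n = 139 pairs and, as a larger illustrative count, 175 (the evaluable number the SAP gives for primary endpoint 2, not a planned QOL count). The completers' SD is held at 30.

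**Formulas.**

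- Completer bias: b = m × D.
- If the true all-subject mean is 2.8 and the missing show zero improvement, the completer mean is 2.8 / (1 − m), so b = 2.8 × m / (1 − m).
- One-sided error: the probability that a noncentral t with n − 1 degrees of freedom and noncentrality b√n / 30 exceeds the 97.5% t quantile.

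**Case A, missing subjects show zero improvement.**

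- m = 10%: b = 2.8 × 0.10 / 0.90 = 0.31
- m = 20%: b = 2.8 × 0.20 / 0.80 = 0.70

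**Case B, missing subjects average 7.2 points below completers.**

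- m = 10%: b = 0.10 × 7.2 = 0.72; completers 3.52, missing 3.52 − 7.2 = −3.68
- m = 20%: b = 0.20 × 7.2 = 1.44; completers 4.24, missing 4.24 − 7.2 = −2.96

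At a true mean of 2.8, case B therefore means that the missing subjects deteriorate.

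| Case | Missing | Bias (points) | Error, 139 pairs | Error, 175 pairs |
|---|---|---|---|---|
| A | 10% | 0.31 | 3.3% | 3.4% |
| A | 20% | 0.70 | 4.6% | 4.9% |
| B | 10% | 0.72 | 4.7% | 5.0% |
| B | 20% | 1.44 | 8.1% | 9.2% |

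**Direction.** With the sign of D reversed (better-off subjects missing), b is negative and the error falls below 2.5%. If the missing average exactly 2.8, b is zero.

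**At the planned effect.** With 139 completers averaging 10, the half-width is 1.977 × 30 / √139 = 5.03 and the lower bound is 4.97. Keeping the completers' standard error, the bound falls to 2.8 when m × D = 4.97 − 2.8 = 2.17. That is D = 21.7 points at 10% missing and 10.8 points at 20%.

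**The case against.** The best defence is that a random cause means missing at random in the technical sense. Standard multiple imputation relies on that assumption, so using it only where the assumption is credible is conventional. This stands as far as it goes: the term is undefined, and a reader who infers that the trigger is simply back to front goes further than the text allows. It also follows that running standard imputation regardless of cause would not cure missingness that depends on the unseen 12-month score. What the defence does not supply is a plan for that case. The fallback to completers needs a stronger assumption than imputation does.

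Other limits also stand:

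- A reader might infer that sensitivity analyses depend on multiple imputation. They do not. LOCF and average replacement are imputation too, and neither is tied to a random cause. The gap arises only when nothing is imputed, although the content of the sensitivity analyses is unspecified throughout.
- A reader might infer that completers will overstate improvement. The documents give no missing rate and no gap, and the direction is an assumption. LOCF can also err either way, and it would make some use of the 3- and 6-month scores.
- The 10% trigger refers to missing answers and follows text on skipped or double-marked questions. It may not count whole missing questionnaires, which a separate LOCF sentence addresses.
- Because 4.1.3 excludes incomplete pairs without exception, completers may decide even when the cause is judged random.
- At the planned effect, moderate gaps would not overturn success: 21.7 points is a large gap at 10% missing.
- The protocol's own QOL statistics section is not in the text I could read, so the point rests on the SAP.

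**Conclusion.** The point holds in a limited form. SAP 3.3 provides no analysis for secondary endpoint 1 when missingness above the 10% trigger is judged non-random. SAP 4.1.3 then leaves the test to completers unless an optional single imputation is chosen, and under pure exclusion no sensitivity analysis is required. Following the stated rule can give a biased test against 2.8.

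The size depends on assumptions that the documents neither supply nor rule out. The range shown runs from 3.3% to 9.2% against a nominal 2.5%. Its lower part assumes that the missing show no improvement; its upper part requires that they deteriorate and that 20% are missing. The planned 139 pairs are unaffected. The documents do not establish that improvement will be overstated, nor that sensitivity analyses are absent in every case. The change is worth making because the endpoint is formally tested and the remedy is cheap.

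**What to change.** In SAP 3.3, for secondary endpoint 1:

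1. Define the 10% trigger so that it counts whole missing 12-month questionnaires as well as missing answers.
2. Remove the random-cause condition. Above the trigger, run multiple imputation of the 12-month physical function score from the baseline, 3-month and 6-month scores, whatever the assessed cause.
3. Because standard imputation does not correct not-at-random missingness, add a delta-adjusted tipping-point analysis. Lower the imputed changes in steps and report the shift at which the lower bound falls to 2.8.
4. Reword the final sensitivity sentence so that these analyses apply whether missing subjects are imputed or excluded.
5. Reconcile 3.3 with 4.1.3 by stating which analysis decides the endpoint and which ones support it.

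The cost is SAP wording and a few analysis runs on scores already being collected, with no new subjects or visits. The estimate may be less favourable or its interval wider.
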